### Amendment 1, version 2.0 (21-Dec-2021)

The 15-Apr-2021 version of the protocol was amended to expand the population to include 6- to 11-year-old participants. Other principal changes included changing the primary objective from safety to efficacy, adding pregnancy and contraception requirements, adding a maximum dose of 170 mg, updating the number of planned participants from 15 to 25, and clarifying that the efficacy endpoints will be presented by PH1, PH2, or PH3 subgroups.

This amendment is considered to be substantial based on the criteria set forth in Article 10(a) of Directive 2001/20/EC of the European Parliament and the Council of the European Union.

Section # and Name	Description of Change	Brief Rationale
Title Page Sponsor Signature Page 1.1. Synopsis 1.2. Schema 1.3. Schedule of Activities 2.1. Study Rationale 3. Objectives and Endpoints 4.1. Overall Design 4.2. Scientific Rationale for Study Design 4.3.1. PK/PD Model for Dose Selection in Pediatric Participants (Birth to 11 Years) 5.1. Inclusion Criteria 6.2.1. Handling and Accountability 6.2.3. Preparation and Administration 6.4. Study Intervention Compliance 7.1.1. Discontinuation of Study Intervention Stopping Rules for Individual Participants 8.1.4.1. Pediatric Quality of Life Inventory 8.3.5. Pregnancy 9.2. Sample Size Determination 9.6. Safety Review Committee (SRC) 10.2. Appendix 2: Clinical Laboratory Tests 10.4. Appendix 4: Contraceptive and Collection of Pregnancy Information (New) 10.5. Appendix 5: Liver Safety: Suggested Actions and Follow-up Assessments 10.7. Investigator Signature Page	Expanded population to include 6- to 11-year-old participants: 1. Updated Study title and study description 2. Updated average spot Uox-to-creatinine ratio inclusion criteria to include values for 6 to 11 year olds 3. Removed word the word 'young' from the phrase 'in neonates, infants, and young children with PH' 4. Added in details regarding dose selection for 6- to 11-year-olds 5. Clarified that 6- to 11-year-olds may have home dosing performed by caregivers or home nurses 6. Updated QoL assessment text to account for 6- to 11-year-olds 7. Clarified that is still required to have 60 days' worth of data from children aged 2 to 5 years old prior to enrolling participants < 2 years 8. Updated liver safety suggested actions and follow-up 9. Added contraception and pregnancy guidelines	1. To update upper age limit to 11 years of age 2. To account for the correct values for 6- to 11-year-olds 3. Children up to 11 years old can now be enrolled 4. Although the dose is the same, the dose selection for 6- to 11-year-olds was separate from the 0 to 5 year olds 5. For older children, it may be possible for caregivers to administer the study drug at home. 6. To account for the questionnaires to be used by 6- to 11-year-olds 7. For participant safety, it is required to review data from children aged 2 to 5 prior to enrolling participants < 2 years 8. Added liver safety suggested actions and follow-up for 6- to 11-year-olds 9. To account for 6- to 11-year-olds who may be of childbearing potential
1.1. Synopsis 3. Objectives and Endpoints 4.2. Scientific Rationale for Study Design 9.4.2. Primary Endpoints 9.4.3.1. Efficacy Endpoints	Updated the primary endpoint to efficacy based upon spot urinary oxalate-to-creatinine ratio; safety endpoint was moved to secondary	To support regulatory objectives for the DCR-PHXC clinical development program

Section # and Name	Description of Change	Brief Rationale
1.1 Synopsis 4.1. Overall Design 4.3.1. PK/PD Model for Dose Selection in Pediatric Participants (Birth to 11 Years) 6.1. Study Intervention(s) Administered	Added a maximum dose of 170 mg	To ensure the dose in children does not exceed the maximum dose given to adult participants across the program
6.1. Study Intervention(s) Administered	Clarified for participants $\geq 6$ months of age at Screening, the dose will remain constant throughout the study (i.e., the dose administered on Day 1 will be the dose administered at all following visits regardless of any change in body weight)	Clarification
1.1. Synopsis 1.2. Schema 4.1. Overall Design 9.2. Sample Size Determination	Updated number of planned participants from 15 to 25: 1. Added new number of expected participants aged 6 to 11 years old 2. Added goal of enrolling approximately 15 participants with PH1	1. To account for additional participants aged 6 to 11 years old 2. To help achieve regulatory goals related to PH1
1.2. Schema 1.3. Schedule of Activities	Clarified in the schedule of activities table that 12-lead ECG should be assessed at Day 30 (noted in Administrative Letter 1, dated 07 June 2021)	Clarification
5.1. Inclusion Criteria	Corrected the inclusion criterion related to serum creatinine cut off for participants aged less than 12 months to be below the 97.5 th percentile of a healthy population (noted in Administrative Letter 3, dated 07 July 2021)	This inclusion criterion is based upon the Boer et al 2010 article, which presents the 97.5 th percentile serum creatinine
1.1. Synopsis 3. Objectives and Endpoints 9.4.3.1. Efficacy Endpoints	Clarified that the secondary efficacy endpoint related to normalization of spot urinary oxalate-to-creatinine ratio includes participants with spot urinary oxalate-to-creatinine ratio $\leq$ the ULN or $\leq 1.5 \times$ ULN at any time point	This endpoint will include the percentage of participants who had spot urinary oxalate-to-creatinine ratio $\leq$ the ULN or $\leq 1.5 \times$ ULN

Section # and Name	Description of Change	Brief Rationale
1.3. Schedule of Activities 2.3.2. Pediatric Burden Assessment 8.2.5. Echocardiogram with Doppler	Clarified that if for an individual participant the echocardiogram cannot be performed without sedation, the echocardiogram should not be performed (noted in Administrative Letter 4, dated 20 August 2021)	The intent of the protocol is that the echocardiogram will not involve any invasive procedures
2.3.4. Risk Management	Clarified details surrounding the SRC review	Clarification
2.1. Study Rationale 2.2.3.1. Clinical Studies of Nedosiran	Added preliminary findings from Study DCR-PHXC-201 and status updated of Study DCR-PHXC-104	To provide updated information
4.1. Overall Design	Clarified that a substantial amendment will be submitted when the data are available to support enrollment for applicable cohorts before any participants < 2 years of age are enrolled.	Clarification
6.5. Concomitant Therapy	Clarified that the requirement to have a stable dose of pyridoxine for 3 months prior to the study did not apply to those under 3 months of age; for such participants, the timeframe requirement for stable dose is relative to their age	It is not possible for participants under 3 months of age to have had a stable dose for at least 3 months
Title Page	Added the EudraCT Number (noted in Administrative Letter 2, dated 09 June 2021) and the NCT Number	Newly available
2.1. Study Rationale 2.2.3.1. Clinical Studies of Nedosiran	Added preliminary findings from Study DCR-PHXC-201 and status updated of Study DCR-PHXC-104	To provide updated information
2.2.1. Overview of Primary Hyperoxaluria	Clarified that systemic oxalosis can occur in patients with PH3	Newly available literature
1.1. Synopsis 3. Objectives and Endpoints 9.4.2. Primary Endpoint 9.4.3.1. Efficacy Endpoints 9.4.4. Tertiary/Exploratory Endpoint(s)	Clarified that the efficacy endpoints will be presented by PH1, PH2, or PH3 subgroups	To allow analysis of the PH subtypes separately
1.3 Schedule of Activities 8.9. Immunogenicity Assessments	Removed text that stated blood samples for analysis of ADA will be analyzed once a validated methodology is available	The ADA assay is now fully validated

Section # and Name	Description of Change	Brief Rationale
1.3 Schedule of Activities 8.2.2. Physical Examinations	Clarified text regarding physical examination to ensure the physical examination is conducted according to the schedule of activities table	Clarification
8.5. Pharmacokinetics	Removed reference to blood samples collected for measurement of plasma concentrations of nedosiran metabolites	Concentrations of nedosiran metabolites will not be measured from blood samples
2.1. Study Rationale 2.2.1. Overview of Primary Hyperoxaluria	Clarified that a treatment for PH1 has been approved in a limited number of countries	Clarification
1.3. Schedule of Activities 8.1.5. Reporting Fluid Intake	Throughout the protocol, the text 'non-breastfeeding' was updated to 'non-breastfed'	This text is referring to a child that is breastfed
6.5.3. COVID-19 and other Vaccines Administration	Updated text to clarify that no vaccines should be administered in the 7 days prior to or following scheduled administration of study intervention	To allow discernment of AEs related to the administration of other vaccines from those related to administration of study intervention
9.6. Safety Review Committee (SRC)	Added an ethicist as a member of the SRC	To add an additional member given the age of the study population
10.1.1. Regulatory and Ethical Considerations	Corrected the CIOMS International Ethical Guidelines reference to CIOMS VI, 2005	Corrected an error in the previous version of the protocol that referred to the guidance as CIOMS IV
10.1.1. Regulatory and Ethical Considerations	Clarified that applicable privacy laws will be followed	For protection of participant privacy
10.1.3. Informed Consent Process	Added language stating participants must be informed of any new information that arises during the course of the study which might be relevant to their willingness to continue in the study and addressed changes in age related to ICF and clarified that as children and adolescents age, they must be re-consented to the appropriate ICF based on current age	To ensure participants are provided with necessary information to make an informed decision about continuing participation in the study
Protocol Amendment Summary of Changes 10.8. Protocol Amendment History	New section added to describe amendment summary of changes	To accommodate amendment summary of changes
Additional editorial changes and minor clarifications were made throughout the protocol.		

No tables entries found.

Version History

This Statistical Analysis Plan (SAP) for study NN7022-PHYOX8 (Dicerna protocol number DCR-PHXC-203) is based on the protocol version V4.0, dated 23-Feb-2023.

SAP Version	Date	Change	Rationale
V2.0	12-Jan-2024	Update age groups for analysis from (0-5, 6-11) to (0 - <2, 2-< 6, 6-<9, 9-11)	Update age groups for analysis following FDA sNDA feedback.
V2.0	12-Jan-2024	Replace the categorical age groups with continuous age as covariate for MMRM modelling in Section 4.2.2	Considering that there are limited number of patients within each updated age group, continuous age variable may be used as a covariate in MMRM modelling.
V2.0	12-Jan-2024	Add sensitivity analysis on the ratio of spot urinary oxalate-to-creatinine ratio to the ULN in Section 4.2.3	Perform additional sensitivity analysis to adjust for the any potential confounding effect of natural maturity on spot urinary oxalate-to-creatinine ratio following FDA sNDA feedback.
V2.0	12-Jan-2024	Update MITT definition to include all PH types	Efficacy will be summarized by PH type.
V2.0	12-Jan-2024	The safety analysis of interim analysis will be based on Safety Analysis Set	All safety data will be included in the interim analysis following FDA sNDA feedback.

List of abbreviations

Abbreviation	Definition
AE	adverse event
AESI	adverse events special interest
ATC	anatomical therapeutic chemical
AUC	area under the curve
BLQ	below the limit of quantitation
BSA	body surface area
CRF	case report form
CS	clinically significant
CSR	clinical study report
ECG	electrocardiogram
eCRF	electronic case report form
EDC	electronic data capture
eGFR	estimated glomerular filtration rate
HR	heart rate
HRQOL	health related quality of life
IC or ICF	informed consent or informed consent form
ICH	International Council for Harmonization
LLOQ	lower limit of quantitation
MedDRA	Medical Dictionary for Regulatory Activities
MITT	modified intent-to-treat
N	number
PD	pharmacodynamic

Abbreviation	Definition
PE	physical examination
PH	primary hyperoxaluria
PK	pharmacokinetic
PKAP	pharmacokinetic analysis plan
PT	preferred term
QOL	quality of life
RR	respiratory rate
SAE	serious adverse event
SAP	statistical analysis plan
SAS®	a software system used for data analysis
SD	standard deviation
SOC	system organ class
TEAE	treatment-emergent adverse event
WHO	World Health Organization
WHO-DD	World Health Organization drug dictionary

1 Introduction

This statistical analysis plan (SAP) describes the planned analysis and reporting for Dicerna protocol number DCR-PHXC-203 (A Phase 2 Open-Label Multicenter Study to Evaluate the Efficacy, Safety, and Pharmacokinetics of Nedosiran in Pediatric Patients from Birth to 11 Years of Age with Primary Hyperoxaluria and Relatively Intact Renal Function), protocol amendment V4.0, dated 23-Feb-2023.

The planned analyses identified in this SAP may be included in clinical study reports (CSRs), regulatory submissions, or future manuscripts. Also, post-hoc exploratory analyses not identified in this SAP may be performed to further examine study data. Any post-hoc or unplanned, exploratory analysis performed will be clearly identified in the final CSR.

This SAP is an *a priori* plan. It will be finalized and signed off prior to clinical database lock of study DCR-PHXC-203.

Specifications of tables, figures, and listings (TFL) and other specifications not included in this SAP will be described in the mock TFL.

1.1 Objectives, Endpoints, and Estimands

1.1.1 Objectives and Endpoints

Objectives	Endpoints
Primary	

 To assess the efficacy of nedosiran in neonates, infants, and children with PH and relatively intact renal function based upon eGFR and serum creatinine 	
 Percent and absolute change from Baseline to Month 6 in spot urinary oxalate-to-creatinine ratio in PH1, PH2, or PH3 participant subgroups
Secondary	

 To characterize the safety of nedosiran in neonates, infants, and children with PH and relatively intact renal function based upon eGFR and serum creatinine 	
 The incidence and nature of TEAEs and SAEs Change from Baseline in 12-lead ECG, physical examination findings, vital sign assessments, and clinical laboratory tests

 To characterize the PK of nedosiran in neonates, infants, and children with PH and relatively intact renal function based upon eGFR and serum creatinine 	
 Plasma PK parameters for nedosiran and/or its metabolites, including C_{max}, AUC_t and AUC_{∞} (if estimable)

 To assess the efficacy of nedosiran in neonates, infants, and children with PH and relatively intact renal function based upon eGFR and serum creatinine 	
 Percentage of participants with spot urinary oxalate-to-creatinine ratio \leq the ULN or $\leq 1.5 \times$ ULN at any time point through Month 6 in PH1, PH2, or PH3 participant subgroups

 To evaluate the effect of nedosiran on eGFR in neonates, infants, and children with PH and relatively intact renal function based upon eGFR and serum creatinine 	
 Change from Baseline in eGFR at Month 6 (only in participants ≥ 12 Months of age at Screening) in PH1, PH2, or PH3 participant subgroups
Tertiary/Exploratory	

 To assess the effect of nedosiran on plasma oxalate in neonates, infants, and children with PH and relatively intact renal function based upon eGFR and serum creatinine 	
 Percent and absolute change in plasma oxalate over time in PH1, PH2, or PH3 participant subgroups

 To assess the effect of nedosiran on stone events in neonates, infants, and children with PH and relatively intact renal function based upon eGFR and serum creatinine 	
 Change from Baseline in annualized stone event rate in PH1, PH2, or PH3 participant subgroups

 To evaluate the effect of nedosiran on QoL assessments in neonates, infants, and children with PH and relatively intact renal function based upon eGFR and serum creatinine 	
 Change from Baseline in the Pediatric Quality of Life Inventory (PedsQL™) in PH1, PH2, or PH3 participant subgroups

 To evaluate the effect of nedosiran on productivity loss of caregivers for neonates, infants, and children with PH and relatively 	
 Change from Baseline in the Work Productivity and Activity Impairment Questionnaire: Primary Hyperoxaluria V2.0,

Statistical Analysis Plan Study ID: NN7022-PHYOX8	CONFIDENTIAL	Date: Jan 19, 2024 Version: 2.0 Status: Final Page: 12 of 29	Novo Nordisk
Objectives		Endpoints	
intact renal function based upon eGFR and serum creatinine		Clinical Practice Version (WPAI:PH, V2.0, CPV) – Caregiver in PH1, PH2, or PH3 participant subgroups	

1.1.2 Primary Estimand

The primary clinical question of interest is: What is the treatment effect of nedosiran in lowering urinary oxalate excretion (Uox) assessed via percent change from baseline in spot urinary oxalate-to-creatinine ratio at Month 6 in PH1 pediatric participants (birth to 11 years of age) with relatively intact renal function.

For the primary objective, the estimand is defined with five attributes:

- Treatment condition of interest is the monthly nedosiran administration.
- The target population is PH1 pediatric participants (birth to 11 years of age) with relatively intact renal function.
- The endpoint is percent change from baseline at Month 6 in spot urinary oxalate-to-creatinine ratio.
- The intercurrent events (ICEs) include treatment discontinuation for any reasons and will be handled by the treatment policy strategy.

[figure not shown]
Population-level summary is the percent change from baseline at Month 6 estimated by Mixed-effect Model Repeated Measures (MMRM) approach.

Rationale for estimand: The primary estimand assesses the treatment benefit of nedosiran in lowering urinary oxalate-to-creatinine ratio that can be expected in clinical practice, provided that the treatment adherence in the study reflects what would be seen in clinical practice.

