### 2.3.3. Benefit Assessment

The biological relationship between urinary oxalate supersaturation and the subsequent calcifications in kidney and extra-renal organs has been well established ([Hoppe et al., 2009](#); [Hoppe, 2012](#); [Cochat & Rumsby, 2013](#)). The degree of hyperoxaluria has been shown to predict the development and severity of nephrocalcinosis and is described as a risk factor for ESRD in patients with PH ([Zhao et al., 2016](#)).

As increased urinary oxalate is an independent risk factor for the development of calcium oxalate crystallization, a reduction in oxalate excretion should lower the risk of calcium-oxalate supersaturation and the subsequent negative consequences on the renal system and beyond. Several researchers have demonstrated that pre-emptive liver transplantation normalizes oxalate

excretion and stabilizes or improves kidney function in long-term follow-up if no systemic oxalosis is present ([Kemper et al., 1998](#); [Galanti & Contreras, 2010](#); [Perera et al., 2011](#)).

Results from nonclinical studies of nedosiran demonstrated that a reduction of hepatic *Ldha* mRNA lowered or eliminated excess oxalate production in the livers of PH model mice and protected the kidney from calcium oxalate crystal deposition and the resultant damage. Based on results achieved in the murine models of PH, administration of nedosiran to participants with PH, who do not have systemic oxalosis, is expected to result in a measurable reduction in urinary oxalate.

Results from the completed Study DCR-PHXC-101 are summarized in Section [2.2.3.1](#) and demonstrate that single-dose administration of nedosiran can reduce the urinary oxalate burden in participants with PH1 and PH2 and potentially decrease the risk for the development of calcium oxalate crystallization.

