### **2.3.5. Overall Benefit:Risk Conclusion**

At present, no therapies are approved by regulatory authorities for the treatment of patients with PH2 or PH3. Lumasiran, a treatment for PH1, is approved in a limited number of countries, including the European Union. A number of supportive therapies are also used in an attempt to mitigate some of the effects of the disease, but affected patients are at considerable risk of serious complications like renal stones, nephrocalcinosis, renal failure, and systemic tissue damage due to oxalate deposition. Combined liver-and-kidney transplantation is the only causative therapy but is associated with short- and long-term complications as well.

Thus far nedosiran treatment has shown potential benefit to reduce or prevent the excess oxalate production in the liver. If sustained, this could eliminate the need for a liver transplantation.

The potential risks with nedosiran include low elevations of liver function tests, muscle damage, and stimulation of pattern recognition receptors (e.g., Toll-like receptors) leading to cytokine release, inflammation, and ISRs. These risks can be monitored and should be reversible after drug discontinuation. The results from the completed study, DCR-PHXC-101, demonstrate the potential for nedosiran to bring patients into a near-normal or normal range of their 24-hour Uox values. Continuous risk-benefit assessments will be conducted by the Sponsor, the Medical Monitor of the CRO, and the SRC on an ongoing basis.

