### **6.5. Concomitant Therapy**

Any medication or vaccine (including over-the-counter or prescription medicines, vitamins, and/or herbal supplements) that the participant is receiving at the time of enrollment or receives during the study must be recorded along with:

- Reason for use
- Dates of administration, including start and end dates
- Dosage information, including dose and frequency

The Medical Monitor should be contacted if there are any questions regarding concomitant or prior therapy.

Participants taking pyridoxine (vitamin B6) must have been at a stable dose for at least 3 months (or as applicable for those less than 3 months of age) prior to Day 1 and must remain on the same stable dose throughout the study. Dose adjustments for interval weight gain are acceptable.

Participants should avoid taking vitamin C supplements, including multivitamins, for 24 hours prior to and during the timeframe when spot urine samples are collected. Other concomitant medication may be considered on a case-by-case basis by the Investigator in consultation with the Medical Monitor (if required).

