#### **6.5.1. Prohibited During the Study**

Participation in any other clinical study involving an IMP is prohibited during this study.

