**Discontinuation from study intervention does not mean discontinuation from the study.**

Remaining visits and study procedures should be completed as indicated by the SoA.

See the SoA for data to be collected at the time of intervention discontinuation and follow-up and for any further evaluations that need to be completed.

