### 8.1. Efficacy Assessments

#### 8.1.1. Spot Urine Collection

Oxalate is a dicarboxylic acid that is a normal end-product of metabolism. Most oxalate in the body is produced in the liver. Humans lack an enzyme to degrade oxalate, and thus it must be eliminated by the kidney. In individuals with PH, mutations in the *AGXT*, *GRHPR*, or *HOGAI* gene result in the overproduction of oxalate by the liver, which causes increased oxalate excretion by the kidneys.

The primary measurement of oxalate in the urine will be via spot urine collection. The second morning void is thought to offer the least variability in terms of Uox/ creatinine.

Urine samples will be collected for the determination of Uox and creatinine. Six spot urine samples (3 of which must be second morning void) will be collected over a 3-day period during Screening. Baseline is defined as the average of the 6 screening values.

Four on-treatment spot urine samples (2 of which must be second morning void) will be collected over a 2-day period on a monthly basis.

Participants should avoid consuming vitamin C, including multivitamins, in the 24 hours preceding urine collection.

Any participant who prematurely discontinues study intervention should perform 4 spot urine collections as directed by the Medical Monitor.

Complete instructions for the spot urine collection, including in infants, will be provided in the Urine Collections Instructions.

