### **Study Intervention Interruption/Discontinuation**

**Study drug must be interrupted** if any of the following criteria are met (applies to participants with normal and elevated transaminases at baseline):

- ALT or AST  $> 8 \times$  ULN
- ALT or AST  $> 5 \times$  ULN for 2 weeks or longer
- ALT or AST  $> 3 \times$  ULN in association with total bilirubin  $> 2 \times$  ULN and/or clinical jaundice or other signs of liver dysfunction (hepatomegaly, pruritus, bleeding, etc).

As children can have LFT elevation from viral infections and medications, an investigation of potential alternative causes (acetaminophen use, EBV, CMV infection, etc) and physical examination should be conducted, and the participant should be closely monitored for clinical progression. **If no alternative etiology is identified, the participant should be discontinued from the study, even if the participant has a normal physical exam.**

If an alternative, reversible cause of transaminase elevation has been identified, and the physical examination is normal the medical monitor should be consulted, and study drug may be resumed after the investigator has confirmed the participant's clinical stability and the transaminases are back to  $< 2 \times$  ULN. Transaminases and bilirubin should be monitored at least weekly for 4 weeks after resuming study drug. **If a protocol defined transaminase elevation ( $> 3 \times$  ULN for participants with normal baseline or  $> 2 \times$  baseline for those**

**with elevated baseline) recurs after re-challenge with the study drug the study drug should be permanently discontinued, regardless of the etiology.**

If a participant lives remote from the study site, local testing may be performed, and the test results reported to the Investigator (along with the reference ranges for the local laboratory).

Participants should be monitored at each study visit and instructed to call the Investigator for new or worsening symptoms of clinical hepatitis and/or liver dysfunction. Both symptoms and calls should be captured in dedicated eCRFs.

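### The primary estimand has no rule for values taken after another oxalate-lowering drug is started, so that drug's effect can be credited to nedosiran

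*SAP*

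**What the plan says.** SAP 1.1.2 asks for the effect of nedosiran on the Month 6 percent change in the spot urinary oxalate-to-creatinine ratio in PH1 children, with monthly nedosiran as the treatment condition. On intercurrent events it says: "The intercurrent events (ICEs) include treatment discontinuation for any reasons and will be handled by the treatment policy strategy". The rationale given there concerns adherence in clinical practice. It does not mention replacement of nedosiran by a second drug.

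SAP 4.2.2 fits the MMRM to Months 1 to 6. SAP 4.3.1.1 counts children at or below the ULN, or 1.5 times the ULN, at any time point through Month 6, and summarises eGFR change at Month 6. None of these sets aside values taken after another therapy starts.

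On follow-up, Protocol 7.1.1 states: "Discontinuation from study intervention does not mean discontinuation from the study", and asks for the remaining visits. Protocol 8.1.1 adds: "Any participant who prematurely discontinues study intervention should perform 4 spot urine collections as directed by the Medical Monitor".

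On other therapy, the whole of Protocol 6.5.1 is: "Participation in any other clinical study involving an IMP is prohibited during this study". Section 6.5 leaves other medication to case-by-case decision, 6.5.2 says rescue medicine does not apply, and exclusion criterion 6 (RNAi drug in the last 6 months) applies at entry. Protocol 2.3.5 notes: "Lumasiran, a treatment for PH1, is approved in a limited number of countries, including the European Union".

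**The concern.** In a randomised trial, treatment policy compares two strategies, each with whatever follows. Here there is one arm. If a child stops nedosiran and starts a drug that lowers oxalate by another route, a treatment-policy Month 6 value reflects that drug, yet it is reported as the effect of nedosiran. The error runs in nedosiran's favour.

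The responder count is exposed more directly than the mean, because a single qualifying visit is enough. A child whose only qualifying visit came after the switch would still count. The Month 6 eGFR summary has the same gap.

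A second drug added without stopping nedosiran is not an intercurrent event at all under SAP 1.1.2, so its values also enter unmarked.

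**Working it through.** **Is the path open?**

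1. Stopping drug does not end follow-up (Protocol 7.1.1), and the Schedule of Activities has monthly urine. But 8.1.1 asks those who stop for four collections without fixing when, so a Month 6 value is possible and not assured.
2. Lumasiran is marketed in some regions for PH1. Neither 6.5.1 nor the entry-only RNAi criterion bars it later. Inclusion criterion 5 expects the family to keep the same PH regimen, so starting it runs against the plan without being expressly prohibited.
3. Post-switch values at nominal visits go into the MITT analysis, because no rule removes them.

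**Do the planned sensitivity analyses close it?** SAP 4.2.3 repeats the primary analysis in two sets.

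- EVAL requires six full doses and completion through Day 180. Dose 6 is on Day 150, so EVAL drops every child who stops earlier. That removes the child; it does not estimate the result without the second drug. It also keeps a child who switches after Day 150 or who adds lumasiran to nedosiran.
- PP drops major deviations that affect the efficacy assessment, as adjudicated by the sponsor. Nothing says that starting lumasiran is one, and SAP 4.1.3 classifies deviations only as important or non-important.

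**Size.** The plan gives no effect size, SD or switch rate, and no formal sample size calculation, so it has no figure to reproduce.

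Inputs:
- n = 15, the PH1 goal in the synopsis. As a variant, n = 20, because SAP 4.2.2 uses MITT, which covers all PH types.
- L, the extra fall due to the second drug. Assumed: own Month 6 change of 0% to -20% without it and -50% to -70% with it, so L runs from 50 - 20 = 30 to 70 - 0 = 70 points.
- k, the number of switchers with a Month 6 value.

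With all Month 6 values present, the model mean is close to the arithmetic mean, so the shift is about k × L / n.

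| k | n | L = 30 | L = 70 |
|---|---|---|---|
| 0 | any | 0 | 0 |
| 1 | 15 | 30/15 = 2.0 | 70/15 = 4.7 |
| 1 | 20 | 30/20 = 1.5 | 70/20 = 3.5 |

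Responder rate among 15 PH1 children: one child is 1/15 = 6.7 percentage points at most.

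Precision, for an assumed SD of 20 to 30 points: SE = 20/√15 = 5.2 to 30/√15 = 7.7 points. One switcher's shift is therefore between 2.0/7.7 = 0.3 and 4.7/5.2 = 0.9 of a standard error.

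**How many switchers?** In Study DCR-PHXC-201, also six months long, 33 of 35 completed treatment (Protocol 2.2.3.1). Scaled to 15 children, 15 × 2/35 = 0.9 would stop for any reason, and only some of those would switch and stay under observation. Zero or one is the realistic count.

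**The case against.** The strongest reply is that the scenario is rare and already partly covered. Families are expected to keep the regimen stable. Concomitant medications are listed, so a switcher would be visible. EVAL excludes early stoppers. The study is descriptive, and SAP 1.1.2 gives a reason for treatment policy. All of this is true, and it limits the size. It does not supply a rule for the primary estimate, and in an open-label study the choice would otherwise be made with the data in view.

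A reader might infer that any child who fails on nedosiran will be scored as a nedosiran response. The documents do not support that:

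- The primary endpoint is a mean percent change, so nothing is scored as a response there.
- The mandatory individual stopping rules in Protocol 7.1.1 concern safety and pregnancy, not lack of efficacy.
- Many who stop may have no Month 6 value. Withdrawn children leave the study, and an early termination visit is mapped only if it falls 20 to 40 days after the last visit. For children under 6 years with certain liver findings, Protocol 10.6 says: "If no alternative etiology is identified, the participant should be discontinued from the study, even if the participant has a normal physical exam". That sits against the general statement in 7.1.1. The two passages must be reconciled, because treatment policy depends on data collected after stopping.

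A reader might also put dialysis and transplantation beside lumasiran. They are remote: entry requires eGFR of at least 30 (or serum creatinine below the 97.5th percentile in infants) and plasma oxalate of at most 30 µmol/L, and excludes planned transplantation and anticipated dialysis. No passage says that dialysis lowers the urinary ratio.

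Finally, the synopsis figures of 25 enrolled and 20 completing might be read as a 20% switch rate. They describe children who do not complete, not children who switch and stay under observation; Protocol 4.1 and 9.2 and SAP 5 moreover speak of 25 screened.

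**Conclusion.** The gap is real and should be closed. A marketed oxalate-lowering drug can be started after entry, follow-up can continue, and no rule keeps its effect out of the primary mean, the any-time-point responder count or the eGFR summary. EVAL and PP are a partial check only.

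The bias is conditional: a child must switch, remain in the study and give urine at an analysed visit. At the realistic count of zero or one, it is nil, or about 2.0 to 4.7 points on the PH1 mean and up to 6.7 points on the PH1 responder rate. The effect of the second drug and the SD are assumptions. Larger shifts need two or more switchers, which the completion record of DCR-PHXC-201 makes unlikely.

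**What to change.** In SAP 1.1.2, add a second intercurrent event: start of another oxalate-lowering therapy (chiefly lumasiran; also transplantation or dialysis should they occur), with or without stopping nedosiran. Handle it by a hypothetical strategy, and keep treatment policy for plain discontinuation. Then state the data rules:

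- Primary MMRM: set urine ratios after the start date to missing.
- Responder count: ignore post-switch visits but keep the child in the denominator.
- eGFR at Month 6: exclude post-switch values from the summary and list them.
- Sensitivity analyses: the all-data treatment-policy result, and one that scores switchers as no change.

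The last analysis is needed because the missing-at-random model borrows from children who continue nedosiran and may be too favourable for a child who did badly on it.

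The cost is a few sentences and one flag. Medication dates are already recorded under Protocol 6.5; procedure dates would be needed for transplantation or dialysis. The downside is small: a few values are excluded, and the estimate may be slightly less favourable.
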